## 6. Best Response (Objective Response)

The Best Response or Objective Response for the subject is the best Global Response Score that is at least 3 weeks in duration.

Please note the following:

- [Olsen \(2011\)](#) states 4 weeks duration, but this was based on drugs that had 4-week treatment cycles. The intent is that the response should last at least one treatment cycle (based on consult with study investigators who are also co-authors of Olsen (2011)).

- Treatment may continue after first assessment of disease progression (PD) if the investigator is of the opinion that PD needs to be confirmed (see [Section 9.4.1](#)). If PD is not confirmed and subject continues treatment, any subsequent time point assessment of CR/PR will be used in assessing Best Response.

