5 DETERMINATION OF SAMPLE SIZE

The sample size of approximately 70 Stage I - III subjects (including Stage I - III subjects from both the Main Study and the Lead-In part 9µg/kg/day dose group combined) was estimated assuming that the lower bound of the 2-sided 95% Confidence Interval (CI) of ORR exceeding 25% which indicates clinical benefit in persistent and recurrent CTCL. With a sample size of 70, the 2-sided 95% exact Clopper-Pearson confidence interval of an

observed 36% ORR (i.e., 25 subjects with CR+PR among 70 subjects) would be with lower bound of 25% and upper bound of 48%.

Sample size estimates were calculated using PASS 2008 software.

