6.4 Efficacy Assessments

6.4.1 Best Overall Response (BOR) based on GRS

The best overall response (BOR) based on the GRS according to Olsen (2011)¹ criteria is described as follows.

Tumor assessment and response criteria will be according ISCL/EORTC response criteria described in Olsen (2011)¹ criteria. This is a composite measure of tumor burden in skin, lymph node, blood, and viscera. The documented date of CR/PR/SD/PD for GRS will be based on the corresponding mSWAT score assessment date (implemented for IRC assessment by IRC and derived programmatically for Investigator assessment). Assessments showing non-PD after a single PD, or assessments showing non-PD after two consecutive PD evaluations within 7 days of each other, will be included in the determination of BOR. The key points of BOR derivation are described as follows.

- **Complete Response (CR).** BOR of CR can be achieved by the following situations:
 - BOR is CR when the duration between the two CRs is ≥ 3 weeks for two consecutive CRs or two CRs with “unknown” or “missing” assessments in between.

The documented start date of CR is defined as the date of mSWAT score assessment date corresponding to the initial CR.

- **Partial Response (PR).** When BOR of CR is not achieved, BOR of PR can be achieved by one of the following situations:
 - BOR is PR when the duration between the two responses (PR or CR) is ≥ 3 weeks for two consecutive PRs, the order of CR, PR, or the order of PR, CR, without intervening of SD/UNK or missing assessments.
 - BOR is PR when the duration between the two responses (PR or CR) is ≥ 3 weeks for two PRs, or the order of PR, CR, with up to two intervening SD assessments in between.
 - BOR is PR when the duration between the two responses (PR or CR) is ≥ 3 weeks for two PRs, the order of CR, PR, or the order of PR, CR, with “unknown” or “missing” assessments in between.

The documented start date of PR is the date of mSWAT score assessment date corresponding to the initial PR or CR

- **Stable Disease (SD).** When BOR of CR/PR is not achieved, BOR of SD can be achieved by the following:
 - If subject at least once had an overall timepoint evaluation of CR/PR/SD that was recorded ≥ 3 weeks after the first dose of study drug.

- **Progressive Disease (PD).** When BOR of CR/PR/SD is not achieved, if subject at least once had an overall time point evaluation of PD, then the BOR is PD.

The date of documented PD is:

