6.4.3 Best Overall Response (BOR) using Prince (2010)²

The IRC will also assess timepoint tumor responses using Prince (2010)² criteria. The BOR based on Prince criteria at subject level will be derived. BOR will fall into the following categories: CR+CCR (Clinical Complete Response), PR, SD, PD, and UNK.

The key point regarding Prince (2010)² criteria is that, according to Prince (2010)² criteria, the documented response (i.e., CR, CCR, PR) required confirmation by two additional tumor burden assessments over a period of at least 6 weeks. Documented responses for all end points had to be confirmed at three consecutive visits (i.e., maintained for 6 weeks after the initial documentation).

Assessments showing non-PD after a single PD, or assessments showing non-PD after two consecutive PD evaluations within 7 days of each other, will be included in the determination of BOR.

The details of derivation can be found in the ADaM Data Specification document.

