6.5.1 Primary Efficacy Analysis

The primary endpoint is the ORR based on Olsen (2011)¹ criteria, using response assessment data by IRC. The ORR is the proportion of subjects achieving a BOR of confirmed CR or PR. The Primary Efficacy Analysis Set will be used for analysis.

The 2-sided, exact 95% CI of ORR will be calculated using the Clopper-Pearson method. The treatment will be considered efficacious and demonstrating the clinical benefit of E7777 if the lower bound of the 2-sided 95% exact CI of the observed ORR exceeds 25%.

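### SAP 6.4.1 accepts a PR interrupted by up to two SD readings as a confirmed response in the primary ORR; the protocol's definition of Objective Response asks for a response that lasts at least 3 weeks.

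*SAP*

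**What the plan says.** **Protocol, Appendix 4, section 6.** "The Best Response or Objective Response for the subject is the best Global Response Score that is at least 3 weeks in duration". The note beneath explains why 3 weeks replaces the 4 weeks of the published criteria: "The intent is that the response should last at least one treatment cycle". Nothing there provides for SD readings inside the 3 weeks.

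**SAP 6.4.1.** The 3 weeks become a minimum distance between two responses. One route to PR is two consecutive responses with nothing between them. A second route is "two PRs, or the order of PR, CR, with up to two intervening SD assessments in between". A third allows unknown or missing assessments in between, without a stated limit. The start date follows the first reading: "The documented start date of PR is the date of mSWAT score assessment date corresponding to the initial PR or CR". SAP 6.4.2 carries the same derivation over to skin response.

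**SAP 6.5.1.** "The ORR is the proportion of subjects achieving a BOR of confirmed CR or PR", by independent review. Success requires that the "lower bound of the 2-sided 95% exact CI of the observed ORR exceeds 25"%.

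**SAP 8.1 and revision history.** Section 8.1 names the clinical benefit rate and two analysis sets, then points to the revision history. That table presents the best-response additions as clarification. It refers in general terms to further response scenarios and itemises four topics: the confirmation interval, the date of response, missing or unknown readings, and two PDs within 7 days. The SD allowance is not among them.

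**The concern.** The protocol attaches the 3 weeks to the response; the SAP attaches them to the gap between two readings. A subject who crosses the PR line at one visit, falls back to SD at the next one or two, and crosses it again is a responder under the SAP. On the plain wording of Appendix 4, section 6, neither PR has been shown to last a cycle.

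The SAP does not treat SD this way throughout. It allows no SD between two CRs, or between a CR and a later PR. For the alternate response criteria it states: "Documented responses for all end points had to be confirmed at three consecutive visits". The exception covers only PR-PR and PR-CR, and no reason is given.

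At stake is the responder definition of a single-arm trial judged on one exact confidence limit. If that definition widens between protocol and SAP without being listed as a change, a reader of the result cannot tell how many responders depend on it.

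**Working it through.** **1. The plan's own figure.** SAP section 5 states that an "observed 36% ORR (i.e., 25 subjects with CR+PR among 70 subjects) would be with lower bound of 25% and upper bound of 48"%. The Clopper-Pearson limits are L = Beta⁻¹(0.025; x, n − x + 1) and U = Beta⁻¹(0.975; x + 1, n − x). With x = 25 and n = 70, L = 24.61% and U = 48.07%. The stated interval reproduces after rounding, but the unrounded lower limit does not exceed 25%.

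**2. The deciding count.**

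| Responders / n | ORR | Exact 95% CI | Lower limit above 25%? |
|---|---|---|---|
| 25/70 | 35.7% | 24.6% to 48.1% | no |
| 26/70 | 37.1% | 25.9% to 49.5% | yes |
| 27/70 | 38.6% | 27.2% to 51.0% | yes |

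The sample size is only approximately 70. The smallest passing count is 26 for n = 69 to 72, and 25 for n = 68.

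**3. What the 3-week spacing tests.** Skin and blood are assessed on Day 1 of each 21-day cycle (Protocol 9.5.2.2).

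- PR-SD-PR: 2 × 21 = 42 days between the two PRs.
- PR-SD-SD-PR: 3 × 21 = 63 days.

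Visit windows of a few days bring neither near 21. In these sequences the SAP's 3-week condition is therefore met automatically and says nothing about how long either PR lasted. An intervening skin SD can be any reading from just under 50% clearance to just under a 25% increase over baseline, provided no new tumors appear in T1, T2 or T4 disease (Appendix 4, Table 2).

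**4. Direction.** Every subject who qualifies by an uninterrupted pair also qualifies under the SAP rule, and the SD bullet adds a further route. The ORR can therefore rise or stay the same, never fall. Let k be the number of responders who qualify only through that bullet. The documents do not give k. At n = 70:

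- 26 responders with k = 1 become 25/70: pass becomes fail.
- 27 with k = 2, or 28 with k = 3, also become 25/70: fail.
- With k = 0 nothing changes.

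**5. Effect on the pass probability.** P(success) = Σ C(70, j) pʲ (1 − p)⁷⁰⁻ʲ for j = 26 to 70. Suppose the ORR under an uninterrupted rule is exactly 25% and the SD bullet adds d points, where d is an assumption.

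| d (points) | p | P(success) |
|---|---|---|
| 0 | 0.25 | 1.6% |
| 1 | 0.26 | 2.6% |
| 2 | 0.27 | 4.1% |
| 3 | 0.28 | 6.1% |
| 5 | 0.30 | 12.1% |

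The nominal one-sided level is 2.5%, so in this setting an addition of 1 point already reaches it.

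**The case against.** **Does SD end a response under the protocol?** The strongest reply is that it does not. The protocol's definition of duration of response dates the loss to the first PD, and Appendix 4, Table 2, places loss of response in the skin under PD. On that reading PR-SD-PR without PD is one continuing response, and the SAP's demand for a second reading adds rigour. The protocol also states no consecutive-visit rule; it speaks only of later assessments needed for confirmation. Further detail sits in a Tumor Assessment Charter and a dataset specification that are not available here. This part stands: a reader might infer that the response was lost at the SD visit, and the documents do not support that. But the duration definition says when a qualified response ends. Appendix 4, section 6, says who qualifies, and its plain wording is not met by a PR that is SD one cycle later.

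**Does duration of response wrongly count SD weeks?** A reader might infer so from the start-date rule. SD time counts for every responder, including PR-PR-SD-SD, because the protocol ends duration at PD and the SAP adds only death.

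**Is the rule undisclosed?** Only the SD allowance is unnamed. The start-date and missing-reading rules are itemised in the revision history, to which 8.1 refers. The documents also set no maximum number of missing readings, so a fixed cap would be a reviewer's preference.

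**Is the comparison with the reference study weakened?** The documents do not state the confirmation rule behind that study's rates, so this cannot be shown. ORR by the alternate criteria is already a planned secondary analysis on the primary set.

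**Is the effect large?** A simulation of assumed borderline subjects (7 visits, no PD, chance 0.15 to 0.20 of a PR at each visit) gives 12-19% responders with two consecutive PRs and 22-35% under the SAP rule if visits are independent. The gain shrinks to 4.5-5.8 points at a visit-to-visit correlation of 0.5, 2.8-3.5 at 0.7 and 1.3-1.5 at 0.9. Reading any of these as a gain in the trial's ORR is unsupported, because the share of such subjects is unknown. If it were 30% (21 of 70, an assumption), correlations of 0.5 to 0.9 imply 21 × 0.013 ≈ 0.3 to 21 × 0.058 ≈ 1.2 responders.

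The allowance is also bounded: at most two SDs, not for CR, and not for CR followed by PR.

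**Conclusion.** The point holds as an unreconciled difference between protocol and SAP in the definition of the primary endpoint. On the plain wording of Appendix 4, section 6, a PR that is SD at the next 21-day assessment does not qualify; under SAP 6.4.1 it can. The protocol's PD-based end of response leaves room for another reading, so the two documents need one rule, stated before the primary ORR is reported.

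The direction is certain: relative to an uninterrupted rule, the allowance can only raise the ORR. The size is unknown and may be zero, because the documents do not say how many subjects qualify only through it. It matters because the margin is one subject: at n = 70, 25 responders fail (24.6%) and 26 pass (25.9%). The pass probabilities in the working rest on assumed increments and illustrate sensitivity; they are not estimates for this trial.

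**What to change.** 1. In SAP 6.4.1, make the primary best-response derivation match Protocol Appendix 4, section 6: CR/PR readings at least 3 weeks apart with no SD or PD between them. The change reaches skin response through 6.4.2. Two qualifying readings that both follow an unconfirmed PD would still count, as the appendix allows.
2. Keep the SD-tolerant rule as a labelled sensitivity analysis of ORR with its exact CI, and state how many responders qualify only through it.
3. List the SD-tolerant rule in SAP 8.1 as a change from the protocol.
4. Report how many responders were confirmed only across unknown or missing assessments.

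The cost is SAP wording and one additional table from data already collected. The downside is that the reported ORR may be slightly lower.

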6.4.2 Best Overall Response (BOR) for Skin Response

BOR for skin response will follow the same approach as described in [section 6.4.1](#) based on timepoint skin response instead of GRS assessment.

6.4.3 Best Overall Response (BOR) using Prince (2010)²

The IRC will also assess timepoint tumor responses using Prince (2010)² criteria. The BOR based on Prince criteria at subject level will be derived. BOR will fall into the following categories: CR+CCR (Clinical Complete Response), PR, SD, PD, and UNK.

The key point regarding Prince (2010)² criteria is that, according to Prince (2010)² criteria, the documented response (i.e., CR, CCR, PR) required confirmation by two additional tumor burden assessments over a period of at least 6 weeks. Documented responses for all end points had to be confirmed at three consecutive visits (i.e., maintained for 6 weeks after the initial documentation).

Assessments showing non-PD after a single PD, or assessments showing non-PD after two consecutive PD evaluations within 7 days of each other, will be included in the determination of BOR.

The details of derivation can be found in the ADaM Data Specification document.

6.5 Efficacy Analyses

All efficacy analyses will be performed on the Primary Efficacy Analysis Set (i.e., in the Stage I – III subjects from Main Study plus the Stage I – III subjects from the 9 µg/kg/day dose group in Lead-In Study), and additionally on Full Analysis Set. Tumor response assessed by IRC based on Olsen (2011)¹ criteria will also be summarized using the Per Protocol Set.

6.5.1 Primary Efficacy Analysis

The primary endpoint is the ORR based on Olsen (2011)¹ criteria, using response assessment data by IRC. The ORR is the proportion of subjects achieving a BOR of confirmed CR or PR. The Primary Efficacy Analysis Set will be used for analysis.

The 2-sided, exact 95% CI of ORR will be calculated using the Clopper-Pearson method. The treatment will be considered efficacious and demonstrating the clinical benefit of E7777 if the lower bound of the 2-sided 95% exact CI of the observed ORR exceeds 25%.

6.5.2 Secondary Efficacy Analyses

6.5.2.1 Duration of Response

The DOR is defined as the time from the date that a confirmed objective response (CR or PR) was first met until the date of documented PD or death due to any cause for those subjects with a confirmed PR or CR. For subjects who did not experience PD or death by the end of data cut off, censoring rules for DOR are the same as those of PFS.

- Duration of objective response (months) = (Date of PD/Death or Censor Date – Date of first objective response + 1) × 12/365.25, for subjects with objective response.

For subjects with confirmed PR or CR, the DOR will be analyzed using Kaplan-Meier (KM) product-limit estimates. Probabilities of DOR ≥ 6 and 12 months will be presented with 2-sided 95% CIs as appropriate, if they can be estimated from the model. The median and quartiles of DOR from KM estimation will be provided with 95% CIs if estimable. The DOR curve from KM method will be provided.

For subjects with confirmed PR or CR, the number and percentage of subjects with DOR ≥ 6 and 12 months will also be summarized as descriptive statistics as appropriate.

The swimmer plot will be plotted demonstrating the treatment duration and timepoint responses over time.

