CT/F-DG-PET-CT scans of skin disease may be performed as necessary for response assessment if the CT acquisition is of diagnostic quality.

- n: Adverse events will be assessed at every visit, until 30 days after the last treatment dose.
- o: Survival follow-up performed every 3 months after discontinuation from study treatment, up to 3 years from end of study treatment.
- p: QoL is to be performed at Baseline, on Day 1 of every cycle during Treatment, at EOT, and during every Tumor Assessment visit during Extension. The QoL will be assessed in Stage I – III Main Study subjects plus the Stage I – III Lead-In subjects from the 9μg/kg/day dose group combined.
- q: Follow-up tumor assessments (except in subjects who discontinued treatment due to PD), immunogenicity and survival follow-up until relapse, or initiation of new systemic anti-cancer therapy, for up to 3 years after EOT.

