6.5.2.5 Duration of Skin Response

The duration of skin response based on the mSWAT score is defined as time from the date when criteria for confirmed skin response (CR or PR) was first met until the date of documented PD or death due to any cause for those subjects with a confirmed PR or CR. For subjects who did not experience PD or death by the end of data cut off, censoring rules for duration of skin response are the same as those of PFS.

Duration of skin response will be analyzed following the same approach in [Section 6.5.2.1](#).

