6.5.3 Other Efficacy Analyses

6.5.3.1 Exploratory Efficacy Analyses

PROGRESSION FREE SURVIVAL

The PFS is defined as the date of first dosing to the date of documented PD or death as a result of any cause (whichever occurs first).

PFS will be analyzed for the Primary Efficacy Analysis Set and Full Analysis Set.

PFS will be analyzed using KM method. The median, quartiles and the PFS rates at 3, 6, 9, 12 months and so on (depending on data adequacy) will be calculated using KM method and

presented with 2-sided 95% CIs if estimable. The cumulative probabilities of PFS will be plotted over time.

The PFS censoring rules in this SAP and definition of progression date will follow the Food and Drug Administration (FDA) “Guidance for Industry Clinical Trial Endpoints for the Approval of Cancer Drugs and Biologics (2007)”

Table 2 Censoring Rules for Analysis of Progression-Free Survival

No.	Situation	Date of Event (Progression/Death) or Censoring	Outcome
1	No baseline tumor or postbaseline GRS assessments	Date of first dose	Censored
2	Progression documented between scheduled visits*	Date of PD by GRS assessment	Event
3	No progression at the time of data cutoff	Date of last adequate GRS assessment prior to or on date of data cutoff	Censored
4	New anticancer treatment started	Date of last adequate GRS assessment prior to or on date of new anticancer treatment	Censored
5	Death before first PD by GRS assessment	Date of death	Event
6	Death between adequate GRS assessment visits**	Date of death	Event
7	Death or progression after more than one missed visit/GRS assessment***	Date of last adequate GRS assessment before missed GRS assessments	Censored

CR = complete response, PD = progressive disease, PR = partial response, SD = stable disease.

Any GRS assessments after new anticancer treatment starts will not be considered in the definition of PFS.

*If subject is not treated beyond initial PD, date of PD should be used. If subject is treated beyond initial PD (per protocol), date of initial PD should be used if consecutive PDs; if there are intervening SD/PR/CR between two PDs, date of the later PD should be used. ** Adequate GRS assessment is assessment of CR, PR, SD and PD at regular interval.

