***More than one missed visits is defined as having the duration between the last tumor assessment and death or PD longer than 44 days which is $(3) \times 2 \times 7 + 3 - 1$ days for subjects on every 3 weeks (-3 days window) for subjects on every 3 weeks tumor assessment schedule during treatment; after date of end of treatment date, 69 days which is $(4+1) \times 2 \times 7 - 1$ days for subjects on every 4 weeks (± 1 week) for 1 year after end of study treatment; 209 days which is $(12+3) \times 2 \times 7 - 1$ days for subjects on every 12 weeks (± 3 weeks) tumor assessment schedule from 1 year after end of study treatment up to 3 years.

The priority of the censoring rules is as follows:

1. If the subject had PD or death, the following sequence will be applied:
 - If a subject did not have a baseline tumor assessment (No. 1), the subject will be censored on the date of first dose. However, if the subject died within 41 days (6 weeks-1day) after first dose and did not receive a new anticancer treatment, it will be

- counted as PFS event at the date of death. If a subject had new anticancer treatment before PD or death (No. 4), the subject will be censored on the date of the last adequate GRS assessment prior to or on the date of new anticancer treatment.
- If a subject missed two or more tumor assessments before PD or death (No. 7), the subject will be censored on the date of the last adequate GRS assessment before PD or death. Note that if a subject is censored by both this criterion and the anticancer treatment criterion, the earliest censoring date will be used.
 - Otherwise, if a subject had an event (No. 2, No. 5, or No. 6), the earliest event date will be used.
2. If a subject did not have PD or death, the censoring date will be the earliest censoring date if the subject met multiple censoring criteria (No. 1, No. 3, No. 4, No. 7).

TIME TO PROGRESSION (TTP)

TTP is defined as the time from the date of first dosing to the date of documented PD or death as a result of CTCL. The same censoring rules, except for death (other cause), as in the analysis of PFS will be applied in calculation of TTP.

TTP will be analyzed following the same approach as for PFS in [Section 6.5.3.1](#).

CLINICAL BENEFIT RATE (CBR)

The CBR is defined as the proportion of subjects who had best overall response of CR or PR or Durable SD by IRC or investigator assessment.

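### Read literally, the SAP applies the PFS censoring rules to duration of response and duration of skin response only for responders without PD or death, so censoring depends on the later outcome

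*SAP*

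**What the plan says.** **DOR (SAP 6.5.2.1).** The interval runs from first confirmed response "until the date of documented PD or death due to any cause for those subjects with a confirmed PR or CR". The censoring sentence follows: "For subjects who did not experience PD or death by the end of data cut off, censoring rules for DOR are the same" as those for PFS.

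**Duration of skin response (SAP 6.5.2.5).** Same event definition and same restriction: "For subjects who did not experience PD or death by the end of data cut off, censoring rules for duration of skin response are" those of PFS.

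**PFS (SAP 6.5.3.1, Table 2 and priority list).** Row 4 censors at "Date of last adequate GRS assessment prior to or on date of new anticancer treatment". Row 7 covers "Death or progression after more than one missed visit/GRS assessment" and censors at the last adequate assessment before the gap. The priority list then has two branches. The first is for subjects who had PD or death, and it includes: "If a subject had new anticancer treatment before PD or death (No. 4), the subject will be censored" at the last adequate assessment on or before that treatment. It treats two or more missed assessments likewise. The second branch is for subjects without PD or death.

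**TTP (SAP 6.5.3.1).** "The same censoring rules, except for death (other cause), as in the analysis of PFS will be applied in calculation of TTP". Nothing limits this to event-free subjects.

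**The concern.** The DOR sentence imports the PFS rules for one group only, responders with neither PD nor death. Responders who have an event fall back on the bare event definition, which does not mention new treatment or missed assessments. The instruction to ignore GRS assessments after new treatment is also written for PFS alone.

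Take two responders with the same response date, last assessment and date of new treatment. They are then handled differently only because one of them later dies or progresses. Kaplan-Meier estimation requires that leaving the risk set at a given time does not depend on what happens afterwards. Here it does: after new treatment, the only responders kept at risk are those already known to have an event.

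At stake are the DOR and skin-duration medians and quartiles, the 6- and 12-month probabilities, and the descriptive counts of responders with durations of at least 6 and 12 months. The same subject can be censored in PFS and be a much later event in DOR.

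**Working it through.** **1. The plan's own figures.** The missed-assessment gaps under Table 2 reproduce: 3×2×7+3−1 = 44 days, (4+1)×2×7−1 = 69 days, (12+3)×2×7−1 = 209 days. The month conversions in SAP 6.5.2.1 and section 9 agree: 12/365.25 = 1/30.4375. The SAP gives no expected DOR, event count or rate of new therapy, so there is no stated result to reproduce. The planning case in SAP section 5 is 25 responders among 70.

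**2. New treatment (No. 4), dates assumed.** Response day 64, last adequate GRS day 190, new treatment day 200. DOR = (end date − response date + 1) × 12/365.25.

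| Later course | PFS | DOR as written | DOR, full PFS rules |
|---|---|---|---|
| Alive, no PD at cutoff | censored day 190 | censored, 127×12/365.25 = 4.2 months | censored, 4.2 months |
| Dies day 800 | censored day 190 | event, 737×12/365.25 = 24.2 months | censored, 4.2 months |

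The subject who dies also counts as having a duration of at least 12 months; the identical survivor does not.

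**3. Missed assessments (No. 7), dates assumed.** Same response and last GRS, no new treatment, off treatment in the first follow-up year, PD recorded on day 290. The gap is 290 − 190 = 100 days, above 69, so PFS is censored at day 190. DOR as written is an event at 227×12/365.25 = 7.5 months. The same responder never assessed again is censored at 4.2 months.

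**4. Can the route occur?** Protocol 9.3.3 stops disease assessment at new systemic therapy, so the later event after such therapy would mostly be death. On whether deaths are then collected, the protocol disagrees with itself:

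- Table 4 footnote o: "Survival follow-up performed every 3 months after discontinuation from study treatment, up to 3 years from end of study treatment", with no stop at new therapy. The Follow-up Period text in 9.5.5.2 also continues until discontinuation from study.
- Table 4 footnote q and section 9.1.4 stop survival follow-up at relapse or new systemic therapy.

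The No. 7 route does not depend on new therapy.

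**5. Size under assumptions.** Simulated responders, 400,000 per scenario. Time to PD, time to new therapy and time from new therapy to the later PD or death are independent and exponential; cutoff is uniform 6 to 36 months after response. For simplicity, censoring is at the start of new therapy. None of these inputs is in the documents. Under this model the full PFS rules recover the true curve. Results as written:

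| True median (months) | Start new therapy before PD | Median from new therapy to later event (months) | Estimated median | 12-month probability (true → estimated) |
|---|---|---|---|---|
| 9 | 20% | 6 to 48 | 8.6 to 9.0 | 0.40 → 0.37 to 0.40 |
| 9 | 50% | 6 | 7.6 | 0.40 → 0.30 |
| 9 | 50% | 24 | 8.9 | 0.40 → 0.39 |
| 12 | 20% | 6 to 48 | 11.1 to 11.9 | 0.50 → 0.47 to 0.50 |
| 12 | 50% | 6 | 9.4 | 0.50 → 0.40 |
| 12 | 50% | 24 | 11.2 | 0.50 → 0.47 |

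Across these scenarios about 1 to 9 of 25 responders are reclassified. A second grid used 10% to 40% starting new therapy and a 12- to 48-month median to death. There a true median of 18.0 becomes 15.3 to 17.7, and a true median of 6.0 becomes 6.0 to 6.2. The 24-month probability falls by at most 0.10 (0.397 to 0.299).

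**6. Direction.** Responders who will have an event stay at risk, event-free, until it occurs, which can lift early estimates slightly. Later on, the retained group contains only events, which pulls the curve down. The net effect is mostly downward.

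**The case against.** The strongest reply is that the opening clause was never meant as a gate. The SAP words such clauses loosely elsewhere: the second PFS branch is for subjects without PD or death, yet it lists No. 7, whose own title describes subjects who had one. PFS is also defined without qualification as time to PD or death, and Table 2 then overrides that, so the unqualified DOR definition does not prove that rows 4 and 7 are excluded. Derivation details are left to programming specifications that are not part of these documents. This stands as evidence about intent. It does not settle the text: nothing in the protocol or SAP restores Nos. 4 and 7 for responders with events, and the unrestricted TTP wording shows the authors could write it the other way.

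Second, if survival follow-up does stop at new systemic therapy, few deaths after it would be recorded and the No. 4 effect shrinks. That stands, and it is why the size is uncertain.

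Third, a reader might infer that time on later therapy is credited to E7777 and so inflates DOR. Individual durations are lengthened, as in the worked case, but they enter as events rather than as censored times. The Kaplan-Meier estimates mostly fall, so the documents do not support a charge of inflation.

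**Conclusion.** The point holds as a defect in a stated rule. SAP 6.5.2.1 and 6.5.2.5, followed literally, make censoring depend on the later outcome, and they depart from PFS and TTP, which agree with each other on Nos. 4 and 7. A programmer following the sentence and one following the probable intent would get different results.

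The effect is limited. It concerns two secondary endpoints that carry no success criterion. A reader might go further and conclude that the duration results must be seriously wrong or that the efficacy claim is compromised; neither follows. The primary ORR analysis does not use these rules. With 20% starting new therapy, the modelled loss in the 12-month probability is about 0 to 0.03. The large shifts (0.50 to about 0.40, median 12 to about 9.4 months) need 50% starting new therapy together with a 6-month median to the later event. All of this rests on assumed rates, exponential times, and post-therapy events being recorded.

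**What to change.** In SAP 6.5.2.1 and 6.5.2.5, delete the opening clause that restricts the censoring rules to subjects without PD or death by cutoff. State instead that all Table 2 censoring rules and their priority order, including Nos. 4 and 7 for subjects with PD or death, apply to DOR and to duration of skin response, consistent with PFS and TTP.

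The cost is one sentence in each section and reuse of the PFS derivation; no new data are needed. The change removes the dependence that the rule itself creates. It does not make the decision to start new therapy uninformative.

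A treatment-policy DOR that ignores new therapy for all responders may be added as a sensitivity analysis. Because disease assessment stops at new systemic therapy, it would rest largely on deaths, so the protocol's conflicting statements on survival follow-up should be reconciled first.
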